## 1. SYNOPSIS

Clinical Study Title:	An open-label study to assess efficacy and safety of a Healing Ointment when used on infants with mild-to-moderate diaper rash
Clinical Trial Number:	GLI.04.US.SL.027
Indication:	Dermatitis
Study population:	Infants at 2- <del>24</del> 35 months of age
Country(ies) Involved and Planned Number of Study Centers:	USA Site: Young Skin [name]
Number of Subjects:	30 subjects to complete
Clinical Study Design:	
This is a single-center, open-label study.
 
Subjects and their parent/legal guardians will report to the site at baseline (day 0) visit, will be given an informed consent form, HIPAA form, photography release form, and medical history form to complete.
 
Subjects will be screened on the basis of the selection criteria for study qualification. Efficacy assessment (skin health, skin smoothness, skin texture), tolerability assessment (dryness, peeling, edema), and self-assessment questionnaire will be performed.
 
Subjects' parent/legal guardians will be instructed to apply the provided Healing Ointment to the buttocks and groin area (if applicable) at every diaper change.
 
Subjects and their parent/legal guardians to return to the site at day 7 (<math>\pm</math> 3 days) and day 21 (<math>\pm</math> 3 days) for follow-ups.
 
For each follow-up visit, investigator will perform objective assessments, tolerability assessments, and photography, if consented. Subjects' parent/legal guardians will perform self-assessment questionnaire.
 
A subject and their parent/legal guardian will be involved in the study for 3 weeks.

Primary Effectiveness Objective and Endpoint:	To evaluate efficacy of a Healing Ointment in skin texture and smoothness in infants 2 to <del>24</del> 35 months old with mild to moderate diaper dermatitis

Secondary Effectiveness Objective(s) and Endpoint(s):	To evaluate subject satisfaction using a Self-Assessment Questionnaire.
Safety Objective and Endpoint	To evaluate safety and adverse events (AEs) throughout the study.
Clinical Study Duration:	The planned clinical study duration (from FSFV to LSLV) is approximately 9 weeks. The planned duration of recruitment is approximately 6 weeks.
Duration of Subject Participation:	Clinical study participation for each subject is 3 weeks
Inclusion criteria:	
The subjects must meet all the following criteria to be eligible for the study:
 
 
1. Infant subjects aged 2 months to 24-35 months
 
2. Females and males
 
3. All Fitzpatrick skin types I-VI
 
4. All races and ethnicities
 
5. Subject diagnosed with mild-to-moderate diaper rash
 
6. Subject with healthy immune systems
 
7. Willing to be photographed at each visit (optional)
 
8. Willing to abstain from use of any other topical diaper rash treatments (ointments, moisturizers, emollients, creams, and wipes) other than the assigned test product and skincare products that have been routinely used on the diaper area during the duration of the study
 
9. Willing to continue using regular brands of face/body cleanser and not to begin use of any new skincare products other than the test product for the duration of the study
 
10. Parent/legal guardian/legal guardians must be at least 18 years old and are willing and able to present proof of legal guardianship
 
11. Parent/legal guardian/legal guardian with ability to read, understand and give consent for participation in the study
 
12. Parent/legal guardians/legal guardians willing to sign a photography release form
 
13. Parent/legal guardian/guardian must agree to adhere to the procedures and requirements of the study and to report to the site on the day(s) and at the time(s) scheduled for the assessments
 

Exclusion criteria:	
The presence of any of the following exclusion criteria excluded a subject from enrollment in the study:
 
 
1. Subject diagnosed with severe diaper rash
 

	
 
2. History of allergy or hypersensitivity to any ingredient of the test product
 
3. Presence of any disease or lesions near or on the area to be treated, e.g., 
 
a. Inflammation, active, or chronic infection in or near the treatment area
 
b. Psoriasis, eczema, rosacea, atopic dermatitis, herpes zoster/herpes simplex, and acanthosis
 
c. Scars or deformities
 
 
 
4. History of coexisting bacterial infections or medical conditions with uncontrolled gastrointestinal diseases and/or bowel movements
 
5. History of severe elastosis and/or excessive sun exposure that, in the opinion of the Investigator, could have affected the outcome of the study
 
6. Planning on having surgeries and/or invasive medical procedures during the course of the study
 
7. Treatment with chemotherapy, immunosuppressive agents, inhaled corticosteroids, immunomodulatory therapy (e.g., monoclonal antibodies or antiviral treatment for human immunodeficiency virus or hepatitis C)
 
8. Current use of topical corticosteroids, topical prescription, or oral antibiotics in the treatment area, or use within last 2 weeks
 
9. Current use of over-the counter topical medications for diaper rash
 
10. History of cancer or previous radiation near or on the treatment area
 
11. Human immunodeficiency virus positive or active hepatitis
 
12. Presence of dermal markings on or near the treatment area that, in the opinion of the Investigator, will interfere with the clinical assessments
 
13. Any medical condition that, in the opinion of the Investigator, would make the subject unsuitable for inclusion (e.g., a chronic or relapsing, disease that may interfere with the outcome of the study)
 
14. Other condition preventing the subject from entering the study in the Investigator's opinion, (e.g., subjects failing baseline assessments, subjects not likely to avoid other cosmetic treatments in the treatment area, subjects anticipated to be unavailable or incapable of understanding the study assessments or having unrealistic expectations of the treatment result).
 
15. Study site personnel, close relatives of the study site personnel (e.g., parent/legal guardians, children, siblings, or spouse), or employees and close relatives of employees at the Sponsor company.
 
16. Participation in any interventional clinical study within 30 days of screening
 

Investigational Products:	Cetaphil Healing Ointment Fla#1748 (ref.:B50H48)
Treatment Area / Treatment Regimen / Mode of Administration	Healing Ointment will be applied topically to the rash area with every diaper change

Effectiveness Assessments:	
Clinical Grading
 

• Efficacy assessment of skin health, skin smoothness, skin texture compared to baseline

 
Self-Assessment Questionnaire
 

• Parent/legal guardian assessment

Safety Assessments:	
Tolerability assessment of dryness, peeling, edema
 
Safety/tolerability assessment at each visit
 
Adverse Event reporting: AEs will be obtained from signs and symptoms reported by the subject or detected during each examination.

Statistical Methods:	
In general effectiveness, safety and baseline characteristics variables will be presented using descriptive statistics within each treatment group and in combination, and graphs as appropriate. Continuous endpoints will be summarized using descriptive statistics, e.g., mean, median, standard deviation, minimum and maximum values. Categorical endpoints will be presented in frequency tables with number and percentage of observations for each level.

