### 4. STUDY OBJECTIVES AND CLINICAL HYPOTHESIS

#### 4.1 Study Objectives

The primary objective of this study is:

- To evaluate benefits of a Healing Ointment in skin improvement in infants 2 to ~~24~~35 months old

The secondary objectives of this study are:

- To evaluate subject satisfaction using a self-assessment questionnaire
- To evaluate safety throughout the study

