#### 4.2 Clinical Hypothesis

The Sponsor's test material will produce a statistically significant improvement in clinical grading of efficacy parameter scores over the course of 3 weeks of use when compared with baseline scores/values. Additionally, the Sponsor's test material will be well tolerated by the subjects, with no statistically significant increases in scores for tolerability/safety parameters at any study time point when compared with baseline scores. Furthermore, the Sponsor's test material will be well perceived by the subjects' parent/legal guardians according to a self-assessment questionnaire at day 1, week 1 and week 3, with a statistically significant proportion of favorable responses compared to unfavorable responses.

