**Table 2. Grading Scale for Tactile Smoothness and Skin Texture**

Parameters	Excellent	Good			Fair			Poor		
	0	1	2	3	4	5	6	7	8	9
Skin Smoothness (tactile)	No palpable skin roughness, drag, and/or surface bumps, depressions	Mild palpable skin roughness, drag, and/or surface bumps, depressions			Moderate palpable skin roughness, drag, and/or surface bumps, depressions			Significantly (severe) palpable skin roughness, drag, and/or surface bumps, depressions		
Skin texture	Smooth visual skin texture	Slightly coarse and uneven skin texture			Moderately coarse and uneven skin texture			Severely coarse and uneven skin texture		

Investigator will grade diaper dermatitis parameter using a 5-point scale where 0 = Normal (no sign) and 4 = Severe (worst possible condition), as described in [Table 3](#).

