## 12. STATISTICAL ANALYSIS

### 12.1 General

All study data will be listed in subject data listings.

All statistical analyses, including summary tables and data listings, will be performed. Confidence intervals will be two-sided and constructed at a confidence level of 95%. Statistical tests will be performed at a significance level of 5%, and  $p$  values will be two-sided.

All endpoints will be summarized descriptively including N, mean, median, standard deviation, minimum and maximum values, for the observed value as well as the change from baseline. Categorical endpoints will be presented in frequency tables with number and percentage of observations for each level.

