### 12.2 Analysis Population

The following populations will be defined:

Intention-to-treat (ITT)	Includes all subjects who receive a test product. Subjects are analyzed based on the as treated principle.
--------------------------	--

Protocol Version: 01

This document contains confidential, proprietary information.

Protocol GLI.04.US.SL.023

CONFIDENTIAL

Per protocol (PP) Includes all subjects in ITT who complete the study after pre-conditioning visit without any deviations that are considered to have substantial impact on the primary effectiveness outcome.

ITT is the primary population for all effectiveness and safety analyses. The primary effectiveness analysis will be repeated using the PP analysis set if there is at least a 10% difference in the number of subjects between the PP and ITT sets.

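### The primary endpoint has no visit or decision rule and is worded differently across sections, the rash grade is in no objective, and six unranked efficacy tests each run at 5%

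*Combined protocol and SAP*

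**What the plan says.** **Target of the study.** The synopsis row for the primary effectiveness objective and endpoint reads "To evaluate efficacy of a Healing Ointment in skin texture and smoothness in infants", followed by the age range and mild to moderate diaper dermatitis. Section 4.1 gives the primary objective as "To evaluate benefits of a Healing Ointment in skin improvement in infants" of the stated ages and does not mention rash. Section 4.2 predicts a "statistically significant improvement in clinical grading of efficacy parameter scores over the course of 3 weeks of use" compared with baseline.

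**What is graded.** The synopsis lists "Efficacy assessment of skin health, skin smoothness, skin texture compared to baseline", and Section 5 names the same three items. Section 10.1 also has three items, but not the same three: smoothness and texture on a 0-9 scale (Table 2), and then "Investigator will grade diaper dermatitis parameter using a 5-point scale" (Table 3). It has no scale called skin health.

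**What is tested.** Table 5 lists smoothness, texture and diaper dermatitis under efficacy, with none marked primary. Section 12.4 tests mean change from baseline at each applicable post-baseline timepoint, and Table 1 places efficacy assessments at Day 7 and Day 21. Under Section 12.1, "Statistical tests will be performed at a significance level of 5" percent and p "values will be two-sided". No ranking or adjustment is given.

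**What depends on a primary outcome.** Section 12.2 keeps out of the per-protocol set subjects with "deviations that are considered to have substantial impact on the primary effectiveness outcome". It repeats the primary analysis in that set if the two sets differ by at least 10%. Section 12.4 closes by allowing a different analysis, thought more suitable, to be recorded in a note to file or in the study report.

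**The concern.** Section 4.2 commits the study to a claim of statistical significance, but no section says which result would establish it. A significant change in either synopsis score, at either visit, could be presented as meeting the objective. The broader wording of Sections 4.1 and 4.2 could also accommodate a rash result. The closing clause of Section 12.4 adds a further choice that may be made after the data are seen.

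The title, the eligibility criteria and the rationale all concern diaper rash. Yet the score that measures it directly is tied to no objective, so the study could meet its stated primary aim on smoothness while the rash grade did not change. The per-protocol rules also cannot be applied as written, because the statistician is not told which score and visit a deviation must affect, or which analysis to repeat.

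**Working it through.** The plan gives no power, effect size, standard deviation or family-wise error rate, so there is no stated figure to reproduce.

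**Inputs from the documents**
- Efficacy scores tested: 3 (Table 5)
- Post-baseline visits: 2, Day 7 and Day 21 (Section 9, Table 1)
- Level: 0.05 two-sided per test (Section 12.1), so 0.025 in the improvement direction
- Sample size: 30 completers (Synopsis, Section 6.1)

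**Assumption.** The documents give no correlation among the change scores. A common correlation from 0 to 0.9 is used.

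**Number of tests.** 3 × 2 = 6. Counting only the two scores in the synopsis: 2 × 2 = 4.

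**Chance of at least one significant result when nothing changes, independent tests**
- Six tests, either direction: 1 − 0.95^6 = 0.265
- Six tests, improvement only: 1 − 0.975^6 = 0.141
- Four tests, either direction: 1 − 0.95^4 = 0.185
- Four tests, improvement only: 1 − 0.975^4 = 0.096

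**Correlated tests.** Simulated paired t-tests with n = 30, equal correlation and 20,000 runs:

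| Correlation | Six tests, either direction | Six tests, improvement | Four tests, either direction |
|---|---|---|---|
| 0 | 27.0% | 14.2% | 18.5% |
| 0.3 | 24.2% | 12.3% | 17.5% |
| 0.5 | 21.1% | 10.3% | 16.1% |
| 0.7 | 16.7% | 8.6% | 13.4% |
| 0.9 | 11.4% | 5.7% | 9.7% |

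The zero-correlation row agrees with the exact 26.5%, 14.1% and 18.5% within simulation error. The benchmarks for one test are 5% in either direction and 2.5% for improvement.

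**Effect of naming one endpoint.** With 30 pairs, the standardized mean change detectable with 80% power is 0.53 SD for one test at 0.05. It is 0.68 SD if six tests share the level by Bonferroni (0.05/6 = 0.0083). At 90% power the values are 0.61 and 0.76 SD. A single primary test, or a fixed order that starts with one, keeps the smaller detectable change without more subjects.

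**The case against.** The synopsis does name primary scores. A reader might infer that the plan has no primary score at all, or that the rash grade could freely be reported as primary. The documents do not support that: calling the rash grade primary would contradict the synopsis, and Section 4.1 is a broader objective rather than a rival endpoint. What is missing is the visit, the either/both rule, and any link from the synopsis to Sections 4.1, 4.2 and 12.

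A reader might also infer that the rash grade was left out of the study. It was not: Table 3 defines it and Table 5 tests it. Since both lists have three items, skin health may be the rash grade under another label. That is plausible, but no section says so, and the grade would still be in no objective.

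Two further inferences do not stand. One is that many infants would start with no room to improve on smoothness or texture. No entry minimum is set for these scores, but Table 3 includes scattered bumps and moderate dryness at its mild grade, while a smoothness score of 0 requires no palpable roughness or bumps. The documents show no floor problem. The other is that the 0-9 scale is unsuitable because its cited source concerns photodamage. Table 2 supplies its own anchors for roughness and texture.

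On error rates, three points have force. Grades of the same skin on the same infants are probably positively correlated, so 26.5% is the high end of the assumed range and not an expected value. Section 12.1 sets a level per test and promises no family-wise rate. If Section 4.2 means that every efficacy score must improve, there is no inflation. The text does not say so, and one sentence would settle it.

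Finally, this is a small uncontrolled study whose synopsis describes descriptive methods. Section 4.2 nevertheless claims statistical significance, so the test behind that claim has to be fixed.

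**Conclusion.** The concern holds. The synopsis names two primary scores without a visit or decision rule, the other sections state the target differently, and Section 12.2 depends on a primary outcome that Section 12 does not define. The direct measure of the condition is in no objective. Because any of several significant results could be offered in support of the claim in Section 4.2, this is more than a missing detail.

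For false improvement, the realistic size is roughly two to five times the single-test rate: about 6% to 12%, against 2.5%. This rests on no true change, all six tests counting toward success, and an assumed common correlation of 0.9 down to 0.3. Restricting attention to the two synopsis scores reduces the inflation but does not remove it.

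These rates do not describe the study's main vulnerability. Infants enter with active rash and there is no control arm, so natural resolution could make every test significant. Defining the primary endpoint does not cure that.

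**What to change.** 1. State the same primary endpoint and visit in the Synopsis, Sections 4.1, 4.2 and 12.4, and Table 5. The preferred choice is change from baseline to Day 21 in the Table 3 diaper dermatitis grade. Section 12.2 should refer to that endpoint by name.
2. Test the remaining scores in fixed order at two-sided 5%, stopping at the first non-significant result: smoothness at Day 21, texture at Day 21, then the Day 7 scores with the diaper dermatitis grade first.
3. If the sponsor prefers to keep texture and smoothness as primary, require both to be significant at Day 21 and make the diaper dermatitis grade the first secondary endpoint. This needs no adjustment but costs power: if each score has 80% power, joint power lies between 60% (0.8 + 0.8 − 1) and 80%.
4. Replace skin health with the diaper dermatitis grade in the Synopsis and Section 5, or delete it.
5. Limit the closing clause of Section 12.4 to changes documented before outcome data are reviewed.

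The cost is an amendment of wording. Every score is already collected at both visits and no extra subjects are needed. The drawback is that fewer results can be called confirmatory.

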**2. LIST OF ABBREVIATIONS AND DEFINITION OF TERMS**

AE	Adverse Event
CTA	Clinical trial agreement
CTN	Clinical trial number
CV	Curriculum vitae
EC	Ethics Committees
EOS	End of Study
FSFV	First Subject First Visit, i.e. first subject who signs the informed consent form
FST	Fitzpatrick Skin Type
GCP	Good Clinical Practice
GDPR	General Data Protection Regulation
ICF	Informed Consent Form
ICH	International Conference on Harmonization
IFU	Instructions for use
Investigational product	Medical device being assessed for safety or performance in a study. "Investigational product" is the same as "study device", "investigational device", or "investigational medical device."
Investigator	The Principal Investigator (PI) or other qualified person, i.e. sub-Investigator, designated and supervised by the PI at a study site to perform critical study-related procedures or to make important study-related decisions as specified on the signature and delegation log
Investigator file	Essential documents relating to a clinical study as defined in applicable GCP guidance document and maintained by the Investigator.
ISO	International Organization for Standardization
ITT	Intention-to-treat
LSFV	Last Subject First Visit
LSLV	Last Subject Last Visit
PI	Principal Investigator; qualified person responsible for conducting the study at a study site
SAE	Serious Adverse Event
Study products	The products used for treatment in the study
Study site	Institution or site where the study is carried out
Tx	Treatment
WHO	World Health Organization

### 3. BACKGROUND AND RATIONALE

Diaper dermatitis is the most common skin disorder seen in young infants and affects those using diapers. Increased moisture resulting from wearing diapers leads to increased friction and maceration, making the skin more susceptible to damage. Infants with diaper dermatitis can present with erythema, edema, scaling, peeling, papules and dryness, and diagnosis is based on skin findings. Management of diaper dermatitis must both heal damaged skin and prevent rash recurrence. The use of topical emollients is recommended to improve skin barrier function, prevent over-hydration, and provide a barrier between the skin and the diaper, limiting contact with the skin. It is recommended to apply emollients with every diaper change.

Cetaphil® Healing Ointment (Galderma, Dallas, TX) is an Over-the-Counter (OTC) skin protectant that contains 71.5% petrolatum, shea butter to soften, smooth and hydrate, as well as vitamin E to help support moisture barrier function. The Healing Ointment has been clinically proven to hydrate the skin's natural barrier for 48 hours while quickly protecting and healing dry, cracked, irritated skin for visible improvement in 1 week. The product is also hypoallergenic, non-comedogenic, gentle on sensitive skin and accepted by the National Eczema Association. These beneficial properties make Cetaphil® Healing Ointment an ideal candidate as a treatment for diaper rash in infants. This study is to investigate safety and efficacy of Cetaphil® Healing Ointment on infants with diaper rash.

### 4. STUDY OBJECTIVES AND CLINICAL HYPOTHESIS

#### 4.1 Study Objectives

The primary objective of this study is:

- To evaluate benefits of a Healing Ointment in skin improvement in infants 2 to ~~24~~35 months old

The secondary objectives of this study are:

- To evaluate subject satisfaction using a self-assessment questionnaire
- To evaluate safety throughout the study

#### 4.2 Clinical Hypothesis

The Sponsor's test material will produce a statistically significant improvement in clinical grading of efficacy parameter scores over the course of 3 weeks of use when compared with baseline scores/values. Additionally, the Sponsor's test material will be well tolerated by the subjects, with no statistically significant increases in scores for tolerability/safety parameters at any study time point when compared with baseline scores. Furthermore, the Sponsor's test material will be well perceived by the subjects' parent/legal guardians according to a self-assessment questionnaire at day 1, week 1 and week 3, with a statistically significant proportion of favorable responses compared to unfavorable responses.

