### 5. OVERALL STUDY DESIGN

This is a single-center, open-label study to evaluate the efficacy and tolerability of a Healing Ointment when used on infants with mild-to-moderate diaper rash.

Protocol GLI.04.US.SL.023

CONFIDENTIAL

Subjects and their parent/legal guardians will report to the site at baseline (day 0) visit, will be given an informed consent form, HIPAA form, photography release form, and medical history form to complete.

Subjects will be screened on the basis of the selection criteria for study qualification. Efficacy assessment (skin health, skin smoothness, skin texture), and tolerability assessment (erythema, dryness, scaling, peeling, edema) will be performed, and baseline photographs will be taken.

Subjects' parent/legal guardians will be instructed to apply the provided Healing Ointment to the groin and buttocks area at every diaper change.

Subjects' parent/legal guardians will complete Day 1 questionnaire at home. Subjects and their parent/legal guardians to return to the site at day 7 ( $\pm 3$  days) and day 21 ( $\pm 3$  days) for follow-ups.

For each follow-up visit, Investigator will perform assessments and photography. Subjects' parent/legal guardians will perform self-assessment questionnaire.

A subject and their parent/legal guardian will be involved in the study for 3 weeks. The study visits are illustrated in **Error! Reference source not found.**

Protocol GLI.04.US.SL.023

CONFIDENTIAL

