**Table 5. Statistical Analysis Plan**

Evaluation	Change from Baseline	Notes/Interpretation
Efficacy Grading 

Skin smoothness (tactile)

Skin texture

Diaper dermatitis

	Paired t-test; If normality fails, a Wilcoxon signed-rank test will be used.	A decrease in scores indicates an improvement
Tolerability Grading 

Dryness

Peeling

Edema

	Paired t-test; If normality fails, a Wilcoxon signed-rank test will be used.	A decrease in scores or lack of significant increase indicates tolerability/safety of the treatment product
Self-Assessment Questionnaire	N/A	Percentage of favorable and unfavorable responses will be provided for each question

Questionnaires will be tabulated; and the frequency and percentage of all response options will be reported for each question and time point. For questionnaire inquiries without baseline response data, a binomial (sign) test will be performed to test if the proportion of the combined designated favorable responses is equal to the combined designated unfavorable responses for each applicable question. A higher percentage of favorable responses with a significant *p* value indicates positive subject perceptions of the study treatment.

Protocol Version: 01

This document contains confidential, proprietary information.

Protocol GLI.04.US.SL.023

CONFIDENTIAL

A more appropriate analysis may be performed, which will be recorded in biostatistics note to file and/or in the study report.

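### Adverse events are the stated safety endpoint, but the only pre-specified tolerability/safety criterion rests on three skin scores and takes in AEs only where they raise one of those scores

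*Combined protocol and SAP*

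**What the plan says.** The safety row of the synopsis reads "To evaluate safety and adverse events (AEs) throughout the study", and Section 4.1 makes safety a secondary objective.

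The criterion appears in two places. Section 4.2 predicts that the product will be "well tolerated by the subjects, with no statistically significant increases in scores for tolerability/safety parameters at any study time point" compared with baseline. The tolerability row of Table 5 (Section 12.4) adds the interpretation: "A decrease in scores or lack of significant increase indicates tolerability/safety of the treatment product". That row contains dryness, peeling and edema, tested by "Paired t-test; If normality fails, a Wilcoxon signed-rank test will be used". The synopsis gives the same three scores ("Tolerability assessment of dryness, peeling, edema"), as does Table 4. Section 5 gives five: "tolerability assessment (erythema, dryness, scaling, peeling, edema").

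Table 5 has no AE row, and Section 12 does not mention adverse events. What reaches AEs there is general. Section 12.1 has all data listed and all endpoints summarized, and says "Categorical endpoints will be presented in frequency tables with number and percentage of observations for each level". Section 12.2 makes ITT, meaning all who receive product, the primary population for safety analyses. The synopsis says safety variables will be described, and Section 11.2 implies some AE display by keeping diary counts apart from it. Section 13 deals with collecting, grading and reporting AEs, not with analysing them.

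**The concern.** The endpoint named for safety and the measure that decides the safety statement are different things. Table 5 goes beyond local tolerability and attaches the word safety to a non-significant change in three skin scores. A related AE that leaves those scores unmoved has no place in that decision.

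The infants who matter most are also the likeliest to drop out of the test. Section 9.2 lists an AE among the reasons for discontinuation and says treated infants who withdraw are not replaced. It calls for completing a visit CRF only when withdrawal happens at a regular visit. No separate assessment at withdrawal is described, and there is no rule for missing scores. The average score among those who remain can look better because infants who reacted have left. At stake is a statement that safety was shown when a material share of treated infants had related AEs and stopped.

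**Working it through.** **The plan's own figure.** The only one is 30 completers (synopsis; Section 6.1). No power, effect size, SD or AE rate is given, so there is no calculation to reproduce. The figures below show how the criterion behaves, taking n = 30 infants who received product.

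**Inputs from the plan.** Three scores from 0 to 3; paired t-test or signed-rank test on change from baseline; "Statistical tests will be performed at a significance level of 5"%, two-sided; two-sided 95% CIs (Section 12.1).

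**1. Does any AE quantity enter the criterion?** Its terms are the mean changes in dryness, peeling and edema and their p-values. No AE count, rate or threshold appears. AEs outside the three scores give the same result at 0 of 30 and at 30 of 30.

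**2. AEs that do raise a score.** Let k of 30 infants worsen by 1 point while the rest are unchanged. The mean change is k/30 and t = mean / (SD/√30). The exact two-sided signed-rank p is 2 × 0.5^k.

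| k | t-test p | exact signed-rank p |
|---|---|---|
| 3 (10%) | 0.083 | 0.25 |
| 4 (13%) | 0.043 | 0.125 |
| 5 (17%) | 0.023 | 0.0625 |
| 6 (20%) | 0.012 | 0.031 |

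Such AEs can change the result, but up to 3 infants (t-test) or 5 (exact signed-rank) can worsen with the criterion still met. If 10 worsen and 10 improve by 1 point, the mean change is 0 and p = 1.0.

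**3. Withdrawal before the Day 7 visit (assumed counts).** Of 30 treated, 6 stop for a related AE before that visit, so 24 have paired data. In dryness 12 fall by 1 and 12 are unchanged, with the same pattern at both visits. Peeling and edema stay at 0.

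- Mean dryness change = −12/24 = −0.5.
- SD = √(24 × 0.25 / 23) = 0.511; SE = 0.511/√24 = 0.104; t = −4.80 on 23 df; p = 0.00008.
- Exact signed-rank p = 2 × 0.5^12 = 0.0005.
- Peeling and edema: change 0, no increase.

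The criterion is met. With the same scores in those 24, it would be met equally if the other 6 had been lost for reasons unrelated to the product.

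**4. What an AE incidence would show.** Exact (Clopper-Pearson) limits for x of n are the 0.025 quantile of Beta(x, n−x+1) and the 0.975 quantile of Beta(x+1, n−x).

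- 6/30 = 20%: 7.7% to 38.6%.
- 0/30: upper limit 1 − 0.025^(1/30) = 11.6%.
- Chance of seeing at least one AE, 1 − (1−p)^30, at assumed true rates of 1%, 5% and 10%: 26%, 79% and 96%.

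**The case against.** The best defence is that the plan does not ignore AEs. They are a named endpoint, so the general provisions of Sections 12.1 and 12.2 and the synopsis apply to them. Section 11 puts the AE interview and diary first among the safety assessments and adds the tolerability grading to them. Section 13 has clinically relevant worsening of a protocol parameter reported as an AE, and related AEs recorded with severity, action taken and a narrative. Section 12.4 also asks for the percentage of infants who worsened on each parameter.

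This disposes of several stronger readings that a reader might infer:

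- **That Section 12 provides no AE analysis at all.** It provides generic description; what is missing is anything specific to AEs.
- **That the result is the same however many infants have a related AE.** Local AEs that raise a score can change it, as 4 of 30 does under the t-test.
- **That AE percentages will be of events rather than infants.** Section 12.1 speaks of observations without defining the unit, so this is an ambiguity. A yes/no tabulation per infant fits the text equally well.
- **That the scores are declared to be the whole safety evaluation.** Section 4.2 is a hypothesis about tolerability, and the Table 5 note sits on one row. No sentence says AEs will be disregarded.

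What the defence leaves untouched is the criterion itself. AE tables in the report would sit beside a rule that has no AE term and already says safety. An infant withdrawn before the first follow-up would be listed but would not be in the paired test. Section 9.2's promise to use all data up to withdrawal cannot supply a score that was never taken.

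**Conclusion.** The point stands. The only pre-specified tolerability/safety criterion is not built on the named safety endpoint, and it can return safety despite related AEs and withdrawals. If only an AE table were missing, this would be a matter of detail. What needs correcting is a stated rule that can give the wrong answer.

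The size cannot be read from the documents, because they give no expected AE or withdrawal rate. The case of 6 stopping out of 30 is an assumed illustration of how the rule behaves and no forecast. It takes 30 treated infants, withdrawals before any follow-up score, and improvement among those who stay. The exact limits depend only on the counts. Since the plan's 30 refers to completers, the number treated may be larger and the limits correspondingly somewhat narrower.

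**What to change.** 1. In the tolerability row of Table 5, delete safety from the interpretation so that it speaks of local tolerability only. Make the matching change to the parameter wording in Section 4.2.
2. Add an AE row to Table 5: number and percentage of ITT infants (denominator: all who received product) with at least one AE, at least one related AE as defined in Section 13, an SAE, and an AE leading to product stop or withdrawal. Give each an exact two-sided 95% CI.
3. State in Section 12.4 that the safety conclusion rests on these incidences, with the tolerability scores as supporting data.
4. While editing, reconcile the five tolerability scores in Section 5 with the three in the synopsis, Table 4 and Table 5.

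The cost is a few sentences and one table from data already collected; no procedure changes. The drawback is a slightly less favourable safety statement, because even no related AE among 30 infants would be reported with an upper limit of 11.6%.
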